Lab	Time	Status	Tofacitinib N=10	Placebo N=5
		Median		
		Min, Max		
	Baseline	N		
		Mean(SD)		
		Median		
		Min, Max		
	Week 6	N		
		Mean(SD)		
		Median		
		Min, Max		
	Week 12	N		
		Mean(SD)		
		Median		
		Min, Max		
	Week 24	N		
		Mean(SD)		
		Median		
		Min, Max		
	Week 30	N		
		Mean(SD)		
		Median		

Lab	Time	Status	Tofacitinib N=10	Placebo N=5
		Min, Max		
	Week 36	N		
		Mean(SD)		
		Median		
		Min, Max		
	Week 48	N		
		Mean(SD)		
		Median		
		Min, Max		

Data cutoff date: DDMMYY

^[1] The safety population includes all patients randomized to TOFA who received at least one dose of study medication.

Table 35: TOFA Physical Examination Findings. Safety Population [1]

Body System	Time	Tofacitini b N (%)	Placebo N (%)
Head Eyes Ears Nose and Throat	Screening		
	Week 6		
	Week 12		
	Week 24		
Respiratory	Screening		
	Week 6		
	Week 12		
Cardiovascular	Screening		
	Week 12		
	Week 24		
	Week 30		
Abdomen	Screening		
	Week 6		
	Week 24		
Musculoskeletal	Screening		
	Week 6		
	Week 12		

Body System	Time	Tofacitini b N (%)	Placebo N (%)
	Week 24		
	Week 30		
Dermatological	Screening		
	Week 6		
	Week 12		
	Week 24		
	Week 30		
	Week 36		
	Week 48		

Note: Percentages are based on the number of subjects with abnormal findings in the Safety Population. [1] The Safety Population includes all randomized subjects who received at least one dose of study medication. Data cutoff date: DDMMYY

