6.1 Schedule of Events

The schedule of events table provides an overview of the protocol visits and procedures. Section 6 of the protocol provides detailed information on each procedure and assessment required for compliance with the protocol.

The investigator may schedule visits (unplanned visits) in addition to those listed on the schedule of events in order to conduct evaluations or assessments required to protect the well-being of the subject.

	Randomized Treatment Period						Open-Label Treatment Period				Safety FU
Study Visit Date ^a	Screening	Baseline	Week 6	Week 12	Phone Call Week 18	Week 24 ^m	Week 30	Week 36	Phone Call Week 42	Week 48	End of Study Phone Call +30d
Study Drug Dispensed											
Tofacitinib or placebo		X	X	X							
Open-label tofacitinib						X		X			
General											
Informed Consent	X										
Eligibility Review	X										
Medical History	X										
Demographics	X										
Vaccine ^p	X										
Clinical Assessments											
Physical Exam	X		X	X		X	X	X		X	
Vital Signs ^c	X	X	X	X		X	X	X		X	
Assessment of Symptoms	X	X	X	X		X	X	X		X	
mRSS ^d	X	X	X	X		X	X	X		X	
CRISS				X		X				X	
European Activity Index	X					X				X	
Physician Assessments ^e	X	X	X	X		X	X	X		X	
Patient Reported Outcomes ^f		X		X		X		X		X	
Adverse Events		X	X	X	X	X	X	X	X	X	X
Pulmonary Function Tests ^g	X			X**FVC only		X				X	
Echocardiogram w/ doppler	X					X					
Laboratory Assessments^h											
PPD/Quantiferon ⁱ	X										
ESR	X		X	X		X	X	X		X	
CRP	X					X				X	
Hepatitis B and C ^j	X										
CBC w/ diff	X	X	X	X		X	X	X		X	
Lipid Panel ⁿ	X		X				X	X			
Comp Panel	X	X	X	X		X	X	X		X	
Pregnancy Test (Urine) ^k	X	X	X	X		X	X	X		X	
Research Assessments											
Biomarkers		X	X			X					

Skin biopsy ^l		X	X								
--------------------------	--	---	---	--	--	--	--	--	--	--	--

^a Screening window will be -65 to 0 days / Remaining Visit windows will be ± 10 days

^b Follow zostervax or shingrix dosing schedule provided on page 20 of this protocol.

^c Blood pressure, Heart Rate, and Temperature. Height and Weight will also be collected at Screening visit.

^d mRSS will be assessed as one of the inclusion criterion

^e Physician Assessments include: Physician's global assessment, Tendon Friction Rub, Swollen and Tender Joint Count, Joint Contractures, and Digital Ulcer assessments.

^f Patient Reported Outcomes include: patient's global assessment, PROMIS-29 2.0, SHAQ-DI, PRO-SRSS and UCLA GIT 2.0

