1.1. Primary Endpoint

Objective: To demonstrate acceptable safety and tolerability of tofacitinib in early dcSSc.

The primary endpoint is the proportion of participants who experience Grade 3 or higher (more severe) adverse events that occur at or before Week 24 (double-blind phase).

1.1.1. Primary Analysis of the Primary Endpoint.

The proportion of subjects in the safety population (see Section 2.1) with at least one Grade 3 or higher adverse event that begins at or before Week 24, the double-blind phase of the trial, will be calculated and compared for each of the study treatment arms.

1.1.2. Secondary Analysis of the Primary Endpoint.

To assess the robustness of the results for the primary analysis, an analysis of the total number of Grade 3 (severe) or higher adverse events that begin at or before Week 24 will also be compared for each of the study treatment arms.

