2.2. Analyses of Primary Endpoint

The primary analysis is a comparison of the percentage of subjects with Grade 3 adverse events that begin within the first 24 Weeks following initiation of study treatment between tofacitinib and placebo. The analysis will be performed on the safety population. The test will be performed using Fisher's Exact Test, given that the largest possible number of patients affected are 10 and 5, respectively, for tofacitinib and placebo. The number and percentage of patients with at least one Grade 3 adverse event will be provided along with Clopper Pearson Exact confidence intervals for proportions at the 90% threshold.

2.2.1. Primary Analysis of the Primary Endpoint.

Proportion of patients with at least one Grade 3 adverse event within the first 24 Weeks

Analysis Set	Safety Population		
Methods	Fisher's Exact Test		
	Clopper Pearson Exact Confidence Intervals		
Results	 Number and percentage of subjects with at least one Grade 3 adverse event in the first 24 weeks 90% confidence interval for proportions P-value from Fisher's Exact Test 		

2.2.2. Secondary Analysis of the Primary Endpoint.

A sensitivity analysis will be performed to assess how the total number of Grade 3 or higher adverse events, rather than just the proportion of patients experiencing the events, affect the conclusions of the analysis of the primary endpoint. The analysis will employ Poisson Regression methodology, offset for time in the study (the lesser of 24 weeks, or withdrawal from the trial).

Analysis Set	Safety Population		
Methods	Poisson Regression offset for time in the study (the lesser of 24 weeks or		
	withdrawal from the trial)		
Dependent	Number of grade 3 or higher adverse events experienced within the first		
Variable	24 weeks on a per patient basis.		
Covariate	Treatment		
Results • Total number of Grade 3 adverse event in the first 24 week			
	 Relative risk of tofacitinib to placebo. 		
	 90% confidence interval for relative risk 		
	P-value for treatment effect		

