3.1.1. Subject Characteristics and Study Conduct

Table 1: TOFA Subject Disposition. All Subjects

Status	Tofacitinib N (%)	Placebo N (%)
ITT Population [1]		
Safety Population [2]		
Open Label Population [3]		
Completed Study Treatment		
Discontinued Study Early		
Reason for Discontinuation		
Subject was determined to be ineligible		
Subject withdrew consent		
Investigator withdrew subject		
Study terminated by Sponsor		
Death		
Lost to follow-up		
Other		
Permanently Discontinued Study Treatment		
Reason for Discontinuation of Study Treatment		
Adverse Event		

Note: Percentages are based on the number of subjects in the Safety Population.

- [1] The ITT population includes all patients randomized to TOFA.
- [2] The Safety Population includes all randomized subjects who received at least one dose of study medication.
- [3] The Open Label Population includes all patients in the Safety Population that have completed 24 weeks (168 Days) of Double-Blind study treatment and not withdrawn from the study.

Data cutoff date: DDMMYY

Listing 1: TOFA Early Termination. ITT Subjects.

Subject ID	Treatment	Reason for Discontinuation	Time on Treatment (Days)	Time in Study (Days)

Conditional Note: No patients have discontinued as of the data cutoff date.

Table 2: TOFA Demographic Characteristics. ITT Population

Variable Statistic or Category	Tofacitinib N=10	Placebo N=5
Age (Years)		
N		
Mean		
SD		

	Tofacitinib	Placebo
Variable Statistic or Category	N=10	N=5
Median	11 20	11 0
Min, Max		
Age, n (%)		
18 to 35 years		
>35 to 55 years		
>55 to 70 years		
Gender, n (%)		
Male		
Female		
Of Childbearing Age		
Not of Childbearing Age		
Hysterectomy		
Tubal Ligation		
Post Menopausal		
Other Reason		
Ethnicity, n (%)		
Hispanic or Latino		
Not Hispanic or Latino		
Race, n (%) [1]		
American Indian or Alaska Native		
Asian		

Variable Statistic or Category	Tofacitinib N=10	Placebo N=5
Black or African-American		
Native Hawaiian or Other Pacific Islander		
White		
Not Reported		
Smoking History, n (%) [1]		
Never		
Past History		
Current Smoker		
No Response		

Note: Percentages are 100*n/N

[1] Subjects reporting more than one race are counted in each of the race categories reported.

Table 3: TOFA Baseline Characteristics. ITT Population

Variable Statistic or Category	Tofacitinib N = 10	Placebo N = 5
mRss at Baseline		
N		

Variable Statistic or Category	Tofacitinib N = 10	Placebo N = 5
Mean		
SD		
Median		
Min, Max		

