# of SAEs		
# of Subjects with SAEs		
# of Subjects		
SAEs per Subject		
% of Subjects with SAEs		

Table 9: TOFA Proportion of Subjects with SAEs by Severity Grade. Safety Population.

System Organ Class Preferred Term	Tofacitinib N=10 n (%) [1]	Placebo N=5 n (%) [1]
Total Events		
Total Subjects With At Least One Event		
Grade 1		
Grade 2		
Grade 3		
Grade 4		
Grade 5		
Grades 3-5		

[1] Percentages are 100*n/N.

The severity grade shown is the greatest grade reported per event for a particular Subject (Grade 1 < Grade 2 < Grade 3 < Grade 4 < Grade 5).

Listing 3: TOFA Listing of SAEs. Safety Population.

Tro	eatment	Subject ID	SAE#	New SAE since (Date of last report)	SAE Brief Description (Verbatim Term)	Treatment Emergent?	SAE Start Date	SAE Stop Date	Days from Start of Study Medication	Severity Grade	Relationshi p to Study Treatment	Outcome	Study Drug Action Taken	Study Drug Stop Date	Study Drug Start Date	

There were no SAEs reported as of the data cutoff date.

Treatment emergent adverse events are AEs that are began after the first dose of study medication.

Note: Double-Blind Treatment is expected to last 24 Weeks (168 Days). Those SAEs that started >= Day 169 are assumed to have occurred during the Open Label phase.

Data cutoff date: DDMMYY

Listing 4: TOFA Listing of Deaths. Safety Population

Treatment	Subject ID	SAE#	New SAE since Aug 4, 2017	SAE Primary Category	SAE Description (Verbatim Term)	Treatment Emergent?	SAE Start Date	SAE Stop Date	Days from Start of Study Medication	Severity Grade	Relationship to Study Treatment	Outcome	Study Drug Action Taken	Treatment Required

Conditional Note: There were no deaths reported as of the data cutoff date.

Treatment emergent adverse events are AEs that began after the first dose of study medication.

Table 10: TOFA Proportion of Subjects with Adverse Events by Primary Category. Safety Population.

Preferred Term	Tofacitinib n (%) [1]	Placebo n (%) [1]

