# of Safety Patients		
# of AEs		
# of Subjects with AEs		
% of Subjects with AEs		
Severity Grade		
No Adverse Events		
Mild		
Moderate		

[1] Percentages are 100*n/N.

The severity shown is the greatest reported per event for a particular Subject (Mild < Moderate < Severe).

Data cutoff date: DDMMYY

Listing 5: TOFA Listing of Treatment Emergent Adverse Events. Safety Population.

Treatment	Subject ID	New AE Since March 5, 2018	CTCAE Classificaiton	AE Primary Category	AE Start Date	AE End Date	Days from Start of Study Medication	Severity	Relationship to Study Treatment	Outcome	Expected / Unexpected	Study Drug Action Taken	SAE?	Worsening of SSC?

Treatment	Subject ID	New AE Since March 5, 2018	CTCAE Classificaiton	AE Primary Category	AE Start Date	AE End Date	Days from Start of Study Medication	Severity	Relationship to Study Treatment	Outcome	Expected / Unexpected	Study Drug Action Taken	SAE?	Worsening of SSC?

Data cutoff date:DDMMYY

Note: Double-Blind Treatment is expected to last 24 Weeks (168 Days). Those AEs that started >= Day 169 are assumed to have occurred during the Open Label phase.

Table 12: Adverse Events of Special Interest. Safety Population.

Preferred Term Category	Tofacitinib N=10 n (%) [1]	Placebo N=5 n(%) [1]
Total Events		
Total Subjects With At Least One Event		
Herpes Zoster		
Malignancies		
Serious Infections		
Lab Value Abnormalities		
Lymphocytes <500cells mm3		
ANC <500cells mm3		
AST/ALT > 3xULN		
Hy's Law Criteria Met		
Hb drop >2gm/dL		
Increase in HDL/LDL > 50%		
Increase in Serum Creatinine > 50%		

[1] Percentages are 100*n/N. Data cutoff date: DDMMYY

The following set of Figures will be of this format:

[figure not shown]

Figure 1: TOFA Spaghetti Plots of Hemoglobin Over Time by Treatment Figure 2: TOFA Spaghetti Plots of WBC Over Time by Treatment

Figure 3: TOFA Spaghetti Plots of Creatinine Over Time by Treatment

Figure 4: TOFA Spaghetti Plots of Lymphoctyes %Over Time by Treatment

Figure 5: TOFA Spaghetti Plots of Neutrophil % Over Time by Treatment

Figure 6: TOFA Spaghetti Plots of ALT Over Time by Treatment

Figure 7: TOFA Spaghetti Plots of AST Over Time by Treatment

Figure 8: TOFA Spaghetti Plots of Total Cholesterol Over Time by Treatment

Figure 9: TOFA Spaghetti Plots of Triglycerides Over Time by Treatment

Figure 10: TOFA Spaghetti Plots of LDL Over Time by Treatment

Figure 11: TOFA Spaghetti Plots of HDL Over Time by Treatment

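### The SAP ends the double-blind phase at a fixed Day 168, although open-label drug is dispensed at a Week 24 visit that may fall 10 days either side, so some events can be put in the wrong phase

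*SAP*

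**What the plan says.** **Timing of the switch.** In the Protocol 6.1 schedule, open-label tofacitinib is first dispensed in the Week 24 column. Footnote a sets the timing: "Remaining Visit windows will be ± 10 days".

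**Endpoint window.** SAP 1.1.1 counts a subject with a qualifying "adverse event that begins at or before Week 24, the double-blind phase of the trial", so it equates Week 24 with the end of blinded treatment. SAP 2.2 states the analysis in elapsed time: "Grade 3 adverse events that begin within the first 24 Weeks following initiation of study treatment between tofacitinib and placebo". The Poisson offset in SAP 2.2.2 stops at 24 weeks or withdrawal, not at the switch. The adverse event of special interest (AESI) tables use the same 24-week heading.

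**Phase labels.** The note under Listing 5 reads "Those AEs that started >= Day 169 are assumed to have occurred during the Open Label phase". Listing 3 carries the matching rule: "Those SAEs that started >= Day 169 are assumed to have occurred during the Open Label phase".

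**Open Label Population.** Note [3] to SAP Table 1 restricts it to safety-population subjects who "have completed 24 weeks (168 Days) of Double-Blind study treatment and not withdrawn from the study".

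No section of the SAP refers to the date of the first open-label dose.

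**The concern.** The primary endpoint is meant to compare the randomized treatments while subjects are on them. A fixed day count does this only if every subject switches at Day 168, and the visit window lets the switch vary. Two errors can follow.

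- **Early visit.** A placebo subject may start open-label tofacitinib before Day 168. A Grade 3 or higher event between the switch and Day 168 then counts against placebo, although it arose on tofacitinib.
- **Late visit.** A subject still on blinded drug after Day 168 may have an event that is labelled open-label and left out of the 24-week tables. The same can happen to findings in the Week 24 CBC and chemistry sample, which is scheduled for the visit at which drug is switched. Week 18 is a telephone call, so this is the only scheduled sample in the blinded period after Week 12. Protocol 7.1 counts abnormal laboratory findings as adverse events and 7.4 grades them, so they can reach the primary endpoint as well as the AESI tables.

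In addition, a subject who switches in-window before Day 168 takes open-label drug but fails the Open Label Population definition.

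With 10 and 5 subjects, one change of status moves the result a long way.

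**Working it through.** **1. The plan's own figure.** 24 × 7 = 168 days, as the SAP states. With the ±10-day window the Week 24 visit runs from Day 168 − 10 = 158 to Day 168 + 10 = 178, which is 21 possible days.

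**2. Most time that can be misassigned.** Per subject: 10/168 = 6.0%. Placebo arm, if all five switch 10 days early: 5 × 10 = 50 of 5 × 168 = 840 days.

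**3. Expected early-switch time.** The documents give no distribution of visit days, so assume it is uniform over the 21 days and that open-label dosing starts at the visit. The early gap is 10, 9, …, 1 days for visits on Days 158–167 and zero otherwise. Mean = 55/21 = 2.62 days per subject. For five placebo subjects: 5 × 2.62 = 13.1 of 840 days.

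**4. Chance that an event falls in that gap.** Assume a constant hazard that gives a 24-week event probability p. The chance that at least one of five placebo subjects has an event in the gap is 1 − (1 − p)^(13.1/168). The rates are those in Protocol 8.1.

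| p over 24 weeks | Mean gap (13.1 days in total) | All five switch 10 days early (50 days) |
|---|---|---|
| 5% | 0.4% | 1.5% |
| 10% | 0.8% | 3.1% |
| 20% | 1.7% | 6.4% |
| 86% (tofacitinib example) | 14% | 44% |

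The 86% row applies if switched subjects take on the highest tofacitinib rate in the protocol's power examples. Under each row's assumptions these are upper bounds on a change in the primary count, because the event must also be that subject's first at Grade 3 or higher. They do not cover the late-visit direction. Laboratory findings there are detected at the visit itself, so a constant hazard describes them poorly.

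**5. Effect of one reassigned subject.** Two-sided Fisher's exact test, level 0.10:

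| True table (tofacitinib vs placebo) | p | After reassignment | p | Crosses 0.10? |
|---|---|---|---|---|
| 6/10 vs 0/5 | 0.044 | 6/10 vs 1/5 (early switch) | 0.282 | yes |
| 7/10 vs 0/5 | 0.026 | 7/10 vs 1/5 (early switch) | 0.119 | yes |
| 8/10 vs 0/5 | 0.007 | 8/10 vs 1/5 (early switch) | 0.089 | no |
| 9/10 vs 0/5 | 0.002 | 9/10 vs 1/5 (early switch) | 0.017 | no |
| 6/10 vs 0/5 | 0.044 | 5/10 vs 0/5 (late tofacitinib event lost) | 0.101 | yes |

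Moving placebo from 0/5 to 1/5 changes its 90% Clopper-Pearson interval from 0–45.1% to 1.0–65.7%.

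**The case against.** The Day 169 notes are footnotes to listings that also print each event's day from the start of medication. They do not themselves define the primary analysis. That stands, but SAP 1.1.1 and 2.2 apply the same elapsed-time cut to the primary endpoint.

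The protocol's endpoint is events at or before Week 24, with no mention of phase. Against it, leaving out events on Days 169–178 is not an error and gives every subject the same risk window. This also stands. The late-visit problem is a conflict with SAP 1.1.1, which calls that period the double-blind phase.

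The schedule shows when open-label drug is dispensed, not when it is first taken, and Protocol 1.4 places the open-label phase after 24 weeks of blinded treatment. Dosing before Day 168 is therefore allowed by the window but not documented. The drug received changes only for placebo subjects, since the tofacitinib arm stays on the same regimen.

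Four stronger readings are tempting but not supported:

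- A reader might infer that about half the subjects are misassigned, because 10/21 = 48% of uniform visit days fall after Day 168, or that 1 − (11/21)^5 = 96% is the chance of a placebo misassignment. These are chances of a mistimed visit, not of an event in the gap.
- A reader might extend the rule to Week 12 blood samples drawn after Day 84. No section states a Day 84 cut, and SAP 1.2.3 can be read as including the Week 12 visit.
- A reader might argue that an on-time Week 24 visit is already Day 169 if the first dose is Day 1. The SAP does not fix the numbering, and the listing column suggests elapsed days.
- A reader might suppose all laboratory output is affected. Table 33 is by nominal visit, and lipids are not drawn at Week 24.

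**Conclusion.** The inconsistency is real: a fixed 168-day cut stands in for the double-blind phase, while the switch can fall anywhere from about Day 158 to Day 178. The early-switch error is the more serious one, because it credits a tofacitinib event to placebo. Its probability is low: about 0.4–1.7% at 24-week rates of 5–20% and about 14% at 86%. These figures rest on uniform visit days, a constant hazard and open-label dosing from the visit.

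If it happens, one subject can move the primary p-value across 0.10 in some tables but not in others. Protocol section 8 calls p-values hypothesis-generating, which limits the consequence. This is a definition to settle before unblinding, not a flaw that invalidates the analysis.

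**What to change.** Before unblinding, revise the SAP as follows:

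1. End each subject's double-blind period at the date of the first open-label dose. If there is none, use the Week 24 visit or the end of follow-up.
2. In the primary and Week 24 AESI analyses, count events that start after the first blinded dose and before that date, including findings in the pre-switch Week 24 sample.
3. Set the Poisson offset in SAP 2.2.2 to the same date.
4. Define the Open Label Population as subjects with at least one open-label dose.
5. Replace the Day 169 notes under Listings 3 and 5.

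**Cost.** SAP wording and a derivation from dispensing or visit dates; no new assessments are needed. The drawback is unequal risk windows, differing by up to 10 days either side of Day 168. The offset adjusts for this only in the Poisson analysis, because the primary Fisher test has none. Report the fixed 168-day count, censored at the first open-label dose, as a sensitivity analysis.

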2. STUDY OUTCOMES

2.1 Primary Outcomes

The **primary study endpoint** will be the proportion of participants who experience Grade 3 (severe) or higher adverse events that occur at or before Week 24.

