1.2. Secondary Endpoints

1.2.1. Secondary Endpoint. Analyses of the Primary Endpoint Over Time.

The analyses of the primary endpoint described in sections 1.1.1 and 1.1.2 will be repeated at Weeks 12 to assess the time course of the safety profile as defined by the occurrence of Grade 3 or higher adverse events.

1.2.2. Secondary Endpoint. Analyses of the Adverse Events at the Grade 2 Threshold.

The analyses described in sections 1.1.1, 1.1.2 and 1.2.1 will be repeated for adverse events beginning at or before the time point of interest that are assessed as at least Grade 2 (moderate) severity.

1.2.3. Secondary Endpoint. % of Subjects with Adverse Events of Special Interest (AESI).

The proportion of subjects in the safety population experiencing an AESI will be compared between the two study treatment arms. Comparisons will be made for at least one AESI of any type, as well as for each of the events that are considered to be of special interest individually. Separate analyses will be performed for AESIs that occur at or before Weeks 12 and 24. AESIs are defined to be any one of herpes zoster, malignancy, serious infection, lymphocytes <500cells mm³, ANC <500cells mm³, AST > 3xULN, ALT > 3xULN, Hy's Law criteria met, Hemoglobin drop > 2mg/dL, increase in HDL/LDL ratio > 50%, or an increase in serum creatinine > 50%.

1.2.4. Secondary Endpoint. Change from Baseline in the Modified Rodnan Skin Score (mRSS).

Change from baseline in the mRSS total score will be compared between the two treatment arms to assess skin thickness relative to the initiation of study treatment at the various time points. The analysis will be performed separately at Weeks 12 and 24 on subjects in the modified intent-to-treat (mITT) population (see section 2.1).

1.2.5. Secondary Endpoint. Provisional American College of Rheumatology Combined Response Index in Systemic Sclerosis CRISS will be compared between the two treatment arms separately at Weeks 12 and 24 on subjects in the modified intent-to-treat (mITT) population (see section 2.1).

1.2.6. Secondary Endpoint. % of Responders as Defined by the mRSS.

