Table 13: TOFA Proportion of Subjects with Grade 3 (Severe) or Higher SAEs Within the First 24 Weeks. Primary Outcome. Safety Population.

Adverse Events	Tofacitinib N=10 n (%) [1]	Placebo N=5 n (%) [1]
Subjects With At Least One Grade 3 or Higher Event		
90% Confidence Interval [2]		
p-value [3]		

[1] Percentages are 100*n/N.

[2] Poisson Regression, offset for time in study (lesser of 36 weeks or end of study).

Table 14: TOFA Number of Grade 3 (Severe) or Higher SAEs Within the First 24 Weeks. Secondary Outcome. Safety Population.

Adverse Events	Tofacitinib N=10 n (%) [1]	Placebo N=5 n (%) [1]
Total Number of Grade 3 or Higher SAEs		
Relative Risk [2]		
90% Confidence Interval [2]		
p-value [2]		

^[1] Percentages are 100*n/N.

[2] Poisson Regression, offset for time in study (lesser of 24 weeks or end of study).

Data cutoff date: 310CT18

Table 15: TOFA Proportion of Subjects with Grade 3 (Severe) or Higher SAEs Within the First 12 Weeks. Secondary Outcome. Safety Population.

Adverse Events	Tofacitinib N=10 n (%) [1]	Placebo N=5 n (%) [1]
Subjects With At Least One Grade 3 or Higher Event		
90% Confidence Interval [2]		
p-value [3]		

[1] Percentages are 100*n/N.

[2] Clopper Pearson Exact confidence intervals for proportions with at least a Grade 3 SAE.

[3] Fisher's Exact Test Data cutoff date: DDMMYY

Table 16: TOFA Number of Grade 3 (Severe) or Higher SAEs Within the First 12 Weeks. Secondary Outcome. Safety Population.

System Organ Class Preferred Term	Tofacitinib N=10 n (%) [1]	Placebo N=5 n (%) [1]
Total Number of Grade 3 or Higher SAEs		
Relative Risk [2]		
90% Confidence Interval [2]		
p-value [2]		

[1] Percentages are 100*n/N.

[2] Poisson Regression, offset for time in study (lesser of 12 weeks or end of study).

Table 17: TOFA Proportion of Subjects with Grade 3 (Severe) or Higher SAEs Within the First 36 Weeks. Secondary Outcome. Safety Population.

System Organ Class Preferred Term	Tofacitinib N=10 n (%) [1]	Placebo N=5 n (%) [1]
Subjects With At Least One Grade 3 or Higher Event		

System Organ Class Preferred Term	Tofacitinib N=10 n (%) [1]	Placebo N=5 n (%) [1]
90% Confidence Interval [2]		
p-value [3]		

[2] Clopper Pearson Exact confidence intervals for proportions with at least a Grade 3 SAE.

[3] Fisher's Exact Test
Data cutoff date: DDMMYY

Table 18: TOFA Number of Grade 3 (Severe) or Higher SAEs Within the First 36 Weeks. Secondary Outcome. Safety Population.

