System Organ Class Preferred Term	Tofacitinib N=10 n (%) [1]	Placebo N=5 n (%) [1]
Total Number of Grade 3 or Higher SAEs		
Relative Risk [2]		
90% Confidence Interval [2]		
p-value [2]		

[1] Percentages are 100*n/N.

[2] Poisson Regression, offset for time in study (lesser of 36 weeks or end of study).

Table 19: TOFA Proportion of Subjects with Grade 3 (Severe) or Higher SAEs Within the First 48 Weeks. Secondary Outcome. Safety Population.

System Organ Class Preferred Term	Tofacitinib N=10 n (%) [1]	Placebo N=5 n (%) [1]
Subjects With At Least One Grade 3 or Higher Event		
90% Confidence Interval [2]		
p-value [3]		

[2] Clopper Pearson Exact confidence intervals for proportions with at least a Grade 3 SAE.

[3] Fisher's Exact Test

Table 20: TOFA Number of Grade 3 (Severe) or Higher SAEs Within the First 48 Weeks. Secondary Outcome. Safety Population.

System Organ Class Preferred Term	Tofacitinib N=10 n (%) [1]	Placebo N=5 n (%) [1]
Total Number of Grade 3 or Higher SAEs		
Relative Risk [2]		
90% Confidence Interval [2]		
p-value [2]		

[2] Poisson Regression, offset for time in study (lesser of 48 weeks or end of study).

Data cutoff date: DDMMYY

Table 21: TOFA Proportion of Subjects with Grade 2 (Moderate) or Higher SAEs Within the First 12 Weeks. Secondary Outcome. Safety Population.

System Organ Class Preferred Term	Tofacitinib N=10 n (%) [1]	Placebo N=5 n (%) [1]
Subjects With At Least One Grade 2 or Higher Event		
90% Confidence Interval [2]		
p-value [3]		

[1] Percentages are 100*n/N.

[2] Clopper Pearson Exact confidence intervals for proportions with at least a Grade 2 SAE.

[3] Fisher's Exact Test

Table 22: TOFA Number of Grade2 (Moderate) or Higher SAEs Within the First 12 Weeks. Secondary Outcome. Safety Population.

System Organ Class Preferred Term	Tofacitinib N=10 n (%) [1]	Placebo N=5 n (%) [1]
Total Number of Grade 2 or Higher SAEs		
Relative Risk [2]		

System Organ Class Preferred Term	Tofacitinib N=10 n (%) [1]	Placebo N=5 n (%) [1]
90% Confidence Interval [2]		
p-value [2]		

^[1] Percentages are 100*n/N.

[2] Poisson Regression, offset for time in study (lesser of 12 weeks or end of study).

Data cutoff date: DDMMYY

Table 23: TOFA Proportion of Subjects with Grade 2 (Moderate) or Higher SAEs Within the First 24 Weeks. Secondary Outcome. Safety Population.

System Organ Class Preferred Term	Tofacitinib N=10 n (%) [1]	Placebo N=5 n (%) [1]
Subjects With At Least One Grade 2 or Higher Event		
90% Confidence Interval [2]		

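### SAP Tables 13–28, including the primary-outcome shell, are titled for serious adverse events although the endpoints are defined on all adverse events, and Table 13 cites the wrong interval method and time window

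*SAP*

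**What the plan says.** **Endpoint definitions.** Protocol 2.1 sets the primary endpoint as "the proportion of participants who experience Grade 3 (severe) or higher adverse events that occur at or before Week 24". SAP 1.1.1 counts safety-population subjects "with at least one Grade 3 or higher adverse event that begins at or before Week 24". Protocol 2.2 frames the secondary Grade 3+ and Grade 2+ endpoints on adverse events as well, and SAP 1.2.2 covers "adverse events beginning at or before the time point of interest that are assessed as at least Grade 2 (moderate) severity". None of these texts requires the event to be serious.

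**Analysis.** SAP 2.2 and 2.2.1 specify Fisher's exact test and Clopper-Pearson exact 90% intervals for events starting in the first 24 weeks. Poisson regression appears only in SAP 2.2.2, as the sensitivity analysis of event counts at 24 weeks, and in its repeats at other time points (SAP 2.3.2).

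**Shells (SAP 3.1.2).** The Table 13 title reads "Proportion of Subjects with Grade 3 (Severe) or Higher SAEs Within the First 24 Weeks. Primary Outcome". Its confidence-interval row carries marker [2], and that footnote reads "2] Poisson Regression, offset for time in study (lesser of 36 weeks or end of study". The p-value row carries marker [3], but no footnote [3] is printed under the table. The count shells label their row in the style of Table 14, "Total Number of Grade 3 or Higher SAEs". The remaining proportion shells carry the footnote "Clopper Pearson Exact confidence intervals for proportions with at least a Grade 3 SAE" or "Clopper Pearson Exact confidence intervals for proportions with at least a Grade 2 SAE".

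**A smaller wording gap.** SAP 2.2, 2.2.1 and 2.3.1 speak of Grade 3 events for the proportion analysis without adding that higher grades count. SAP 1.1.1 does add it.

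**The concern.** In these documents SAE is a defined term. Protocol 7.2 defines seriousness by outcome (death, threat to life, hospitalization and so on). Protocol 7.3 recognises non-serious adverse events. Protocol 7.4 grades every adverse event for severity, serious or not. Protocol 7.1 allows an abnormal laboratory finding to be an adverse event. A Grade 3 laboratory abnormality that meets no seriousness criterion therefore counts for the endpoint but not for the tables as titled. SAP Listing 5 carries severity and SAE status in separate columns, so a programmer could apply SAE as a filter.

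Safety is the trial's primary objective. A table marked as the primary outcome but limited to SAEs would report a different endpoint, and its error in each arm's rate can go only downward. The between-arm comparison could move either way. Grade 2+ is probably more exposed than Grade 3+, because the protocol's Grade 2 description involves only minimal or non-invasive intervention.

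The footnote error is separate. A Poisson model with a 36-week offset does not give an exact interval for a proportion, and Week 36 lies in the open-label period, when former placebo subjects may be on tofacitinib.

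**Working it through.** **1. Where the SAE wording stands**

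| Element | Tables | Wording |
|---|---|---|
| Titles | 13–28 (16 of 16: eight Grade 3+, eight Grade 2+) | SAEs |
| Row label, count shells | 14, 16, 18, 20, 22, 24, 26, 28 (8 of 8) | SAEs |
| Clopper-Pearson footnote, proportion shells | 15, 17, 19, 21, 23, 25, 27 (7 of 8) | SAE |
| Table 13 below its title | column header and row label | Adverse Events; Event |

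Table 13 therefore contradicts itself as well as the endpoint definition.

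**2. Could the Table 13 footnote have been displaced in the PDF text?** There are eight count shells and eight proportion shells. The text holds 9 Poisson footnotes, 7 Clopper-Pearson footnotes and 7 Fisher footnotes. The one surplus Poisson footnote and the one missing footnote of each other type all fall on Table 13. The two 36-week count shells (18 and 26) have their own Poisson footnotes. Displacement does not explain it.

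**3. The plan's own power figures.** Protocol 8.1 claims at least 80% power for Grade 3+ adverse events at two-sided 10%, with 5 placebo and 10 tofacitinib subjects. Exact power is the sum, over all tables with Fisher p≤0.10, of Bin(x; 10, p_T)·Bin(y; 5, p_P). Results: 80.2% (20% vs 86%), 80.5% (10% vs 79%) and 81.0% (5% vs 74%). The stated power is reproduced by Fisher's test on adverse events, as in the text.

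**4. Weight of one subject.** 1/10 = 10 percentage points on tofacitinib; 1/5 = 20 points on placebo.

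**5. Hypothetical effect on the comparison.** Notation is x/10 tofacitinib vs y/5 placebo. Two-sided Fisher p is the sum of the probabilities of all tables with the same margins that are no more likely than the one observed.

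- 6 vs 0: (210 + 10)/C(15,6) = 220/5005 = 0.044
- 5 vs 0: (252 + 50 + 1)/C(15,5) = 303/3003 = 0.101
- 7 vs 1: (600 + 45 + 120)/C(15,8) = 765/6435 = 0.119
- 7 vs 0: (120 + 45)/C(15,7) = 165/6435 = 0.026

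| As defined (AEs) | p | If restricted to SAEs | p |
|---|---|---|---|
| 6/10 vs 0/5 | 0.044 | 5/10 vs 0/5 (one tofacitinib subject dropped) | 0.101 |
| 6/10 vs 0/5 | 0.044 | 3/10 vs 0/5 (three dropped) | 0.51 |
| 7/10 vs 1/5 | 0.119 | 7/10 vs 0/5 (one placebo subject dropped) | 0.026 |
| 6/10 vs 2/5 | 0.61 | 6/10 vs 0/5 (two dropped) | 0.044 |

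Clopper-Pearson 90% limits are the 0.05 quantile of Beta(x, n−x+1) and the 0.95 quantile of Beta(x+1, n−x). For tofacitinib: 6/10 gives 30.4–85.0%, 5/10 gives 22.2–77.8%, 3/10 gives 8.7–60.7%.

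**6. All 11×6 = 66 possible tables.** Eleven show a higher tofacitinib rate with p≤0.10. Four of them (6/0, 8/1, 9/2, 10/3) lose that when one tofacitinib subject is dropped. Five tables with p>0.10 (6/1, 7/1, 8/2, 9/3, 10/4) reach p≤0.10 when one placebo subject is dropped. On the other side, 11 tables show a higher placebo rate with p≤0.10, and four further tables (1/2, 2/3, 3/4, 5/5) reach p≤0.10 when one tofacitinib subject is dropped.

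**The case against.** The governing text is unambiguous: every definition in the protocol and in SAP sections 1 and 2 rests on adverse events, and SAP 2.2 states the correct methods both in prose and in its method table. The shells also hint at the intended meaning. Tables 13–15 are headed Adverse Events, all eight proportion rows say Event, and Table 9 already has an SAE row for Grades 3–5. Table 13 has no relative-risk row, unlike the Poisson shells, and its footnote matches Table 18's, so it looks like a copying slip. Read this way, the point is a labelling inconsistency and the planned analysis is unchanged.

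The numerical examples can also be challenged. With 5/10 or fewer tofacitinib subjects affected, no table with a higher tofacitinib rate reaches p≤0.10, so in that range the error can neither create nor remove a significant tofacitinib excess. The examples drop subjects from one arm at a time, although the label applies to both. Protocol section 8 treats p-values as hypothesis-generating. Many Grade 3+ events will be serious anyway, since hospitalization features in both definitions.

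Most of this stands as a limit on size: the harm is conditional, and crossing 0.10 triggers no decision. It does not remove the defect. The SAE wording runs through 16 titles, eight row labels and seven footnotes, and the shell labelled as the primary outcome names another event class and another interval method. The shift in the reported rate does not depend on any p-value.

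**Conclusion.** The concern holds. Tables 13–28 contradict the endpoint definitions in the protocol and in the SAP's own text, and Table 13's interval footnote contradicts SAP 2.2 in both method and window. The endpoint itself is correctly defined, so this is an error in the shells that does harm only if outputs follow them. If they do, each subject with a qualifying adverse event but no qualifying SAE lowers the reported rate by 10 points (tofacitinib) or 20 points (placebo), never upward. The comparison may move toward or away from a difference. The total effect cannot be computed, because the documents give no serious share among graded events; the p-value examples are illustrations that assume 10 and 5 analysed subjects. It should be corrected before the SAP is finalised, which protocol section 8 requires before unblinding.

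**What to change.** - In Tables 13–28, replace SAE(s) with AE(s) in all 16 titles, the eight count-shell row labels and the seven Clopper-Pearson footnotes. Keep SAE summaries in Tables 8–9.
- In Table 13, replace footnote [2] with the Clopper-Pearson exact 90% confidence interval and add footnote [3] as Fisher's exact test, both for events beginning at or before Week 24.
- In SAP 2.2, 2.2.1 and 2.3.1, write Grade 3 or higher, in line with SAP 1.1.1.

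The cost is wording edits to the SAP. No new data are needed: Listing 5 already holds both severity and SAE status, so the corrected tables can be checked against it.
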